9.2 Procedures

An untoward event that occurs after screening and before the first dose of investigational product will be recorded as an update to the medical history.

Some events may make the patient ineligible for randomization. Unanticipated events should be reported to the IRB, according to its requirements.

Patients will be questioned at every visit after the first dose until Visit 11 or ET regarding the occurrence and nature of any AEs. All AEs will be reported, whether or not they are deemed to be related to investigational product.

A description of the event or diagnosis including dates, severity, relationship to the investigational product, action taken with the study drug and outcome, and whether or not the event was also serious, must be reported on the AE CRF for each adverse event recorded in the patient's chart.

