3.1 Overall Study Design

This is a multi-center, open-label, two-period cross-over, patient-pilot study comparing DST-0509 to Exjade or Jadenu administered orally once daily (QD) for 28-days in each period, with a 7-day washout before study entry and between treatment periods (see Table 6-1). Patients will be randomized to one of two treatment sequences: DST-0509→Exjade/Jadenu or Exjade/Jadenu→DST-0509 (with subjects who were taking Exjade prior to study start receiving Exjade and those taking Jadenu at study start receiving Jadenu). This study is designed to assess the safety, tolerability, evidence of iron chelating activity, and PK profile of DST-0509 compared to Jadenu or Exjade in inadequately responding patients. Inadequate response to standard chelation therapy is defined from the medical literature [6,7].

Up to 36 patients will be randomized 1:1 into one of two treatment sequences (study arms), of which up to 100% may be on Jadenu or Exjade at study entry, or a mix of the two. The planned randomization will assign up to 18 patients in each of two sequences: Sequence A: DST-0509 crossed to Exjade or Jadenu; Sequence B: Jadenu or Exjade crossed to DST-0509. The comparator treatment will be the patient's current chelation treatment. At the end of the study, patients previously on Jadenu or Exjade will revert to receiving their pre-study medication and dose following a 7-day washout period. A sufficient number of patients will be enrolled so there will be no need to replace study drop-outs. Study duration is approximately 14 weeks for each patient. A Study Flow Diagram is presented after this Synopsis (see Figure 3-1).

Figure 3-1: Study Flow Diagram

Treatment A (28 days) = DST-0509
Treatment B (28 days) = Jadenu/Exjade¹

*Up to 36 patients are planned.

- Subjects taking Exjade prior to study start will receive Exjade (treatment B) in the assigned Period 1 or cross-over Period 2. Those patients taking Jadenu prior to study start will receive Jadenu (treatment B) in the assigned Period 1 or cross-over Period 2. Dosing will be at equivalent (mg for mg) doses of DST-0509 for Jadenu. If crossing over from Exjade to DST-0509, or vice versa, the dose will be scaled to 28 mg/40 mg (DST-0509/Exjade).
- For all patients entering the trial, a 7-day washout is required.

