3.2 Discussion of Study Design

This multi-dose 2-period, 2-arm crossover design was selected to adequately evaluate and compare the safety, tolerability and efficacy of DST-0509 compared to Jadenu and Exjade.

A 7-day washout period will be employed before the first treatment period, in between study treatments and at the end of the study, in order to clear the patient's system of any previous iron chelation treatment.

The choice of the drug strength used was justified based on analytical, pharmacokinetic and safety grounds. Furthermore, this strength was the Reference Listed Drug recommended by the FDA as follows. The FDA approved initial dose of DFX is 20 mg/kg and may be titrated up to 40 mg/kg with the Exjade formulation [1]. The dosing of Jadenu is initially 7 or 14 mg per kg body weight (depending on the indication) orally, once daily [2]. The maximum recommended dosage of DFX as Jadenu is 28 mg per kg body weight orally, once daily [2].

A food effect study involving administration of DFX as Jadenu to healthy subjects under fasting conditions and with a low-fat (fat content <7% of total calories) or high-fat (fat content >50% of total calories) meal indicated that the AUC and C_{max} were slightly decreased after a low-fat meal (by 11% and 16%, respectively). After a high-fat meal, AUC and C_{max} were increased by 18% and 29%, respectively. The increases in C_{max} due to the change in formulation and due to the effect of a high-fat meal may be additive and therefore, it is recommended that DFX as Jadenu should be taken on an empty stomach or with a light meal (contains less than 7% fat content and approximately 250 calories) [2].

Because DFX is rated in the pregnancy category C1, women will be included in the present study, provided they consent to take appropriate measures to prevent pregnancy for at least 28 days prior to the first administration of the study drug, during the study and for at least 30 days after the last dose of the study drug. Additionally, if the participant is using systemic contraceptives, she must use an additional non-hormonal form of acceptable method of contraception during the study and for at least 30 days after the last dose of the study drug.

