7.6 Washout

There will be a 7-day washout period before initial treatment with study drug, a second 7-day washout after the crossover and before treatment with the second study drug, and a third 7-day washout period at the end of the study on Day 63.

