8.5.3 Safety Analyses

Adverse Events

Adverse experiences will be coded using Medical Dictionary for Regulatory Activities (MedDRA, version 20.0 or higher) and summarized by System Organ Class (SOC) and Preferred Term for each treatment group. All AEs will be captured after the first dose through the final visit (Visit 11) or the ET visit.

Adverse events will be summarized by presenting:

- the number and percentage of patients experiencing any AE
- the number and percentage of patients experiencing any AE grouped by SOC
- the number and percentage of patients experiencing any SAE
- the number and percentage of patients experiencing any AE associated with study discontinuation.

Gastrointestinal Adverse Events of Special Interest (GI AESI)

In addition, safety will also include assessing adverse events of special interest (AESI) including selected gastrointestinal AEs of diarrhea, constipation, nausea, vomiting, and abdominal pain.

Other Safety and Tolerability Parameters

At each clinic visit, treatment exposure will be estimated with compliance rates based on patient diary cards and pill counts, and tolerability will be assessed by general enquiry and specific iron chelation tolerability questions as well as by patient diaries concerning tolerability. Study patients will receive a diary to record gastrointestinal (GI) adverse events (AEs) of special interest (AESI) during the course of the study. Patients will be given the Bristol Stool Chart with diary and instructed on its use to help them characterize the nature of the bowel movements. All AE's will be monitored throughout the trial.

Patient safety will be monitored per clinical standard of care including routine laboratory monitoring. This will include monthly CBC, chemistry panel, and urinalysis assessments. Urine will be collected to measure protein: creatinine ratio and serum CRP will be assessed.

Compliance

Patients will be responsible for supplying their own Jadenu or Exjade during the study. Pill counts will be performed at each visit in order to characterize patient compliance (calculated as % doses taken per protocol). Additional measures of compliance will include Investigator enquiry into patient prescription refill records if available, satisfaction with iron chelation therapy (SICT) questionnaire [ref 8; [Appendix D](#)] and use of patient diaries.

Dose reductions

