9 ADVERSE EVENT MONITORING

9.1 Definition

An AE is defined as any untoward medical occurrence in a patient or clinical investigation following the patient's first dose of investigational product that does not necessarily have a causal relationship with this treatment. An AE can be any unfavorable or unintended sign (including an abnormal finding), symptom, or disease temporally associated with the use of a medicinal (investigational) product, whether or not related to the medicinal (investigational) product.

This includes any occurrence that is new in onset or aggravated in severity or frequency from the baseline condition (including the physical examination), or abnormal results of diagnostic procedures (including laboratory test abnormalities).

Events should be considered AEs if they:

- result in discontinuation from the study,
- require treatment or any other therapeutic intervention,
- require further diagnostic evaluation (excluding a repetition of the same procedure to confirm the abnormality),
- are associated with clinical signs or symptoms judged by the Investigator to have a significant clinical impact.

Clinically Significant Laboratory Changes: It is the Investigator's responsibility to review the results of all laboratory tests as they become available. For each abnormal result, the Investigator needs to ascertain whether the abnormality presents a clinically significant change from baseline. If the change is due to the expected course of the patient's underlying disease (e.g., elevated cholesterol in a study of dyslipidemia), it is not considered an adverse event unless the abnormality is more severe than expected. A laboratory test may be confirmed by repeat testing or other diagnostic tests before being considered an adverse event. If the laboratory abnormality is a significant change from baseline for the patient, then it should be considered an adverse event.

An Adverse Event is not:

- A surgical procedure
- A situation where an untoward event did not occur, (e.g. a social hospitalization)
- The disease being studied, unless progression is more severe than anticipated
- Lack of efficacy
- Baseline conditions that have not worsened in severity or frequency
- Clinically significant abnormal laboratory findings or test results related to the disease being studied (unless more severe than expected)

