9.8.1 Serious Adverse Event Reporting

Any SAE which occurs after the first dose is administered until Visit 11 (Day 70) must be reported to Accelovance, Inc. whether or not it is judged related to the investigational product. Accelovance, Inc. must be notified within 24 hours after the site becomes aware of the SAE. Accelovance, Inc. has the responsibility to notify DisperSol of the event.

If the Principal Investigator determines that the event is serious, the following procedures will be followed:

- The Investigator will report the SAE directly to Accelovance, Inc. Accelovance Inc.'s contacts are:

Medical Monitor:

[name]
Medical Monitor
Accelovance, Inc.
[name]
[name]
[contact]
SAE [contact]
[contact]

Project Manager:

[name]
Project Manager II
Accelovance, Inc.
[name]
[name]
Office: [contact]
[contact]
[contact]
[contact]

- The Investigator will provide, at a minimum, the protocol number, patient's initials, patient number, date of the SAE, SAE term and relationship to investigational product. The SAE Report Form should be faxed to [contact] within 24 hours of awareness of the SAE with any supporting data or copies of CRF pages.

- The Investigator will notify the Institutional Review Board (IRB) of the SAE within the timeframe specified by the IRB. An initial report followed promptly by a complete report will be forwarded to the IRB, or in accordance with the IRB policy.

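### The study-imposed chelation stop before Day 1 lies outside AE capture and 24-hour SAE reporting; the two later washouts lie inside it

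*Protocol*

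**What the plan says.** **The washouts.** Section 3.2 states: "A 7-day washout period will be employed before the first treatment period, in between study treatments and at the end of the study". Section 7.6 repeats this ("There will be a 7-day washout period before initial treatment with study drug, a second 7-day washout after the crossover", then a third at the end of the study), and the flow diagram notes in Section 3.1 add: "For all patients entering the trial, a 7-day washout is required". Table 6-1 places the first washout on Days -7 to -1, after consent at Visit 1 and washout instructions at Visit 2, and before randomization on Day 1. The second is on Days 29-35. The third follows the last dose on Day 63.

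**The reporting window.**
- Section 9.1 defines an AE as an occurrence "following the patient's first dose of investigational product".
- Section 8.5.3: "All AEs will be captured after the first dose through the final visit (Visit 11) or the ET visit".
- Section 9.2 says that an untoward event that "occurs after screening and before the first dose of investigational product will be recorded as an update to the medical history". It requires AE questioning only after the first dose, and it asks for severity, relationship, action, outcome and seriousness on the AE form only.
- Section 9.8.1: "Any SAE which occurs after the first dose is administered until Visit 11 (Day 70) must be reported" to the CRO, which must be told within 24 hours of the site becoming aware.

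**The concern.** The first washout is not usual care. These patients are on maximal-dose deferasirox with an LIC above 5 mg Fe/g dw and ferritin above 800 mcg/L, and they stop treatment only because the study asks them to. Harm that arises in that week is harm during a study procedure, yet the protocol treats it as background history.

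Two things are at stake. The first is timely oversight: neither the CRO nor the Medical Monitor has to be told promptly of a serious event in the stop. The second is completeness. Randomization comes after the washout, so a patient whose event prevents randomization becomes a screen failure under Section 7.7. That patient is also outside the Safety Population of Section 8.2, which requires receipt of study medication. The most serious events are the likeliest to end in this way.

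There is a smaller point about grading. The synopsis counts an event that worsens in severity after dosing as treatment-emergent, but no pre-dose severity grade is required for an event that began in the first washout.

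**Working it through.** The point rests on no sample-size, power or alpha figure. For completeness, the one design figure in Section 8.1 reproduces: the chance of at least one diarrhea event at a 12% rate with N=30 is 1 - 0.88^30 = 0.978, against the stated 0.98. It is unaffected by anything below.

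**Step 1. Set the washouts against the reporting window.**

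| Washout | Days | Follows | In AE capture (8.5.3, 9.1)? | 24-hour SAE report (9.8.1)? |
|---|---|---|---|---|
| First | -7 to -1 | Patient's own prescription | No; medical history (9.2) | No |
| Second | 29-35 | Period 1 treatment | Yes | Yes |
| Third | 64-70 | Period 2 treatment | Yes | Yes |

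The third row needs a qualification. Section 9.8.2 says that SAEs with onset after Day 63 or early termination may be reported up to Day 70, where 9.8.1 says they must be. Sections 8.5.3 and 9.2 also end AE collection at Visit 11 or the early termination visit.

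**Step 2. Follow one event through the text.** Take a hospital admission on Day 31. It meets 9.1, goes on the AE form with severity and relationship, and is reported within 24 hours. Now take the same admission on Day -4. It falls outside 9.1 and becomes a history update under 9.2, with no grading required and no 24-hour report. If the patient is not randomized, Sections 7.7 and 8.2 keep the event out of every safety analysis.

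**Step 3. Check whether another provision closes the gap.**
- Table 6-1 marks Adverse Events at Visit 3 (Day 1), but the definition in 9.1 limits that entry to events after dosing.
- Section 7.2 and Table 6-1 schedule medical history at Visit 1 only. The Visit 3 list in 6.3.1 contains no history update.
- The GI and stool diaries are dispensed at Visit 1 and collected and reviewed on Day 1, so they span the washout. They cover five selected GI symptoms and stool form (7.13, 7.14).
- The Day 1 vital signs, examination, ECG and laboratory tests show what is present that day. Section 7.9 files clinically significant pre-dose findings as medical history.
- Section 9.2 sends unanticipated events to the IRB under the IRB's own rules. It names neither the CRO nor the Medical Monitor.

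Each provision captures something. None requires an SAE assessment or an expedited report.

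**Step 4. Size.** Washout days per patient: 7 + 7 + 7 = 21. Share before the window opens: 7 / 21 = 1/3. With the planned maximum of 36 patients: 36 x 7 = 252 of 36 x 21 = 756 washout patient-days. Patients who wash out but are not randomized would add to the 252. With the window opened at Day -7, the share is 0 of 21.

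**The case against.** The strongest reply is that starting at first dose is a deliberate and coherent rule, stated the same way in 8.5.3, 9.1, 9.2 and 9.8.1. The first washout precedes randomization and follows the patient's own drug, whereas the other two are post-dose follow-up of study treatment. The protocol cites nothing to suggest that a 7-day pause causes serious events, and 252 patient-days is a measure of exposure, not of harm. All of this stands. The point is therefore a choice that can be improved, not an internal contradiction.

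A reader might infer more than the text supports in four ways.

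- **That the first washout has no safety monitoring.** It has the history update, the diaries, the Day 1 assessments and the IRB route, and Section 9.2 says that some events may make a patient ineligible.
- **That the three washouts are identical and handled in opposite ways.** They share their length and their origin in the protocol, but not what precedes them.
- **That the crossover safety comparison is biased.** First-washout events occur before randomization, in patients of both sequences alike. An event that begins there is not treatment-emergent unless it worsens after dosing, and Section 9.1 then counts the worsening as an AE.
- **That such events never reach the sponsor's side.** Sections 11.1 and 13.2 provide for CRF entry and for CRF and source review by the CRA. What is missing is mandatory, graded and prompt reporting.

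**Conclusion.** The point holds as a reporting gap for a study-imposed procedure. A serious event on Days -7 to -1 is recorded only as a medical-history update, with no required seriousness, severity or relationship assessment and no expedited report to the CRO or Medical Monitor. The gap covers one third of each patient's scheduled washout days, at most 252 patient-days for 36 patients who receive study drug. This assumes the nominal schedule without visit windows and counts the third washout as Days 64-70. The documents give no event rate for the stop, so no expected number of missed events can be stated.

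The by-treatment TEAE tables and the sample-size reasoning are unaffected. The change is a cheap improvement in safety oversight, not the correction of a statistical error.

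**What to change.** In Sections 8.5.3, 9.1, 9.2 and 9.8.1, start AE recording and 24-hour SAE reporting at the start of the first washout (Day -7). State that this includes patients who are then not randomized. Flag these events as pre-treatment, list them separately and keep them out of the TEAE tables, so that the TEAE definition does not change. Ask about events in the washout at Visit 3 before dosing, where the diaries are already reviewed. Align the synopsis sentence on AE monitoring and the Day 1 pre-dose rule in Section 7.9.

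The cost is protocol wording and slightly more site reporting. Sample size, treatment rules and analysis tables do not change, apart from one added listing.

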5 STUDY TREATMENTS

5.1 Identity of Investigational Product

The investigational product for the open-label crossover study treatment will be DST-0509 supplied in 360 mg, 180 mg and 90 mg film coated tablets supplied by DisperSol Technologies, LLC ([name]; see Investigator's Brochure [9]).

The methods used in, and the facilities and controls used for the manufacturing, processing, packaging, and holding of this drug substance conform with Current Good Manufacturing Practices (cGMP) in accordance with 21 CFR Parts 210 and 211. DisperSol will maintain certificates of analysis for each ingredient, documenting its purity and potency.

The following will be printed on the bottle label: Study ID, Lot/Batch No., placeholders for Site No., Screen No., Patient Initials and Date Dispensed.

Jadenu is commercially available as tablets, and Exjade as tablets for suspension, and both will be ordered by prescription and provided by the patient. Dosing will be at equivalent (mg for mg) doses of DST-0509 or Jadenu. If converting from Exjade to DST-0509, the dose will be scaled for each treatment by 28 mg/40 mg (DST-0509/Exjade).

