6.7 Patient Completion Criteria

For purposes of this study, patients who have not discontinued investigational product early will be defined as study completers; interruption/missed dosing will be discussed with the PI. If the subject does not have the Follow-up (Day 70) phone to confirm washout, the subject will still be considered a completer.

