9.4 Relationship

The Investigator will judge the likelihood that the AE was related to the investigational product according to the following criteria

Not related: There is no temporal or causal relationship to the investigational product.

Related: There is a possible temporal or causal relationship to the investigational product.

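### Adverse-event causality is asked only about the 'investigational product', which section 5.1 defines as DST-0509 alone, so no rule records relationship to Jadenu or Exjade

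*Protocol*

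**What the plan says.** Section 5.1 opens with "The investigational product for the open-label crossover study treatment will be DST-0509 supplied in 360 mg, 180 mg and 90 mg film coated tablets". It then treats Jadenu and Exjade separately: "both will be ordered by prescription and provided by the patient". No other section defines the term.

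The safety rules depend on that term:

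- Section 9.1 confines adverse events to occurrences "following the patient's first dose of investigational product that does not necessarily have a causal relationship with this treatment".
- Section 9.2 says of events after screening that those occurring "before the first dose of investigational product will be recorded as an update to the medical history".
- Section 9.4: "The Investigator will judge the likelihood that the AE was related to the investigational product according to the following criteria". The only answers offered are Related and Not related.
- Section 9.5 asks what action was taken with the investigational product, but its Not Applicable option refers to the study drug.
- Section 6.7: "patients who have not discontinued investigational product early will be defined as study completers".

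Other places are neutral as to sequence. Section 8.5.3 states: "All AEs will be captured after the first dose through the final visit (Visit 11) or the ET visit". The synopsis (Statistical Analyses) plans treatment-emergent events by treatment group, and also by severity and by relationship to study medication.

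**The concern.** The primary objective is safety and tolerability of DST-0509 compared with Jadenu or Exjade. That comparison needs the same recording rules under both treatments: the same start of adverse-event status, and a causality judgment about the drug the patient is actually taking.

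If 'investigational product' means DST-0509, a patient on Jadenu with drug-related diarrhea is never assessed for relationship to Jadenu. A table of related events by treatment group would then compare a column in which investigators attributed events to the drug in hand with a column in which they were not asked to. A second, smaller problem is that the start of adverse-event status would come at different times in the two sequences. Both are rules for what sites write down, so the trial could not recover the missing judgments at analysis.

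**Working it through.** This point is textual. The sample-size figures (98% for at least one and 89% for at least two diarrhea events, 12% rate, N=30) reproduce by the exact binomial as 0.978 and 0.890, and they have no bearing on it. The check is to set the uses of the term side by side.

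**Places where it means DST-0509 only**
- 5.1: names DST-0509 and describes the comparators apart from it.
- 5.2: product is shipped to the site, logged, and returned to the sponsor or its designee. That fits DST-0509 and does not fit a patient's own prescription.

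**Places where it covers either treatment**
- 5.4: the heading concerns administration of investigational product, the text describes all three drugs, and the first dose is on Day 1 and the last on Day 63 for everyone.
- 5.5: product is counted at Visits 3 through 10, and the plural is used.
- 6.5: the Day 70 call is timed from the last dose of it, in either sequence.
- Table 6-1: it is dispensed on Days 1 and 36, with a footnote covering all treatments.

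**Causality.** Take each comparator period under the 5.1 definition:
- Sequence B, Period 1 (Days 1 to 28): no DST-0509 has yet been taken, so the only answer open under 9.4 is Not related.
- Sequence A, Period 2 (Days 36 to 63): the question asks about DST-0509, last taken around Day 28. A Related answer would attribute the event to the earlier drug, yet the event would be tabulated in the comparator period.

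Neither case yields a relationship to Jadenu or Exjade. Comparator exposure affected: up to 36 patients × 28 days = 1,008 patient-days, which is all of it. On the looser meaning, 9.4 still does not say which drug is intended for an event in washout or early in Period 2. Section 9.8.1 uses the same term for the relationship item in the minimum report of a serious event. No section gives a rule for attribution to the comparator.

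**Start of adverse-event status.** Under the 5.1 definition, 9.1 and 9.2 would start the clock for Sequence B at the first DST-0509 dose on Day 36. Days 1 to 28 plus the washout of Days 29 to 35 would fall outside it, for up to 18 patients (18 × 28 = 504 of the 1,008 comparator patient-days). Against that:
- 7.9: findings before Day 1 dosing are history, and new or worsened clinically significant findings at any post-randomization visit are adverse events.
- 8.5.3 and 9.8.1: capture starts after the first dose.
- Table 6-1: adverse events are collected at every visit from Day 1.

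These rules conflict with 9.1 and 9.2 as read with 5.1. They show that Day 1 was very probably intended.

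**The case against.** The best case for the protocol is that its working use of the term covers both periods and that the intent is plain. In 9.2, the sentence on medical history is followed by a remark that some events may make the patient ineligible for randomization. That fits only the time before Day 1. Section 9.2 also has all adverse events reported whether or not they are related, and 7.6 calls both treatments study drug.

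Most of this stands, and it rules out three stronger readings that a reader might infer:

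- *Events in comparator-first patients become medical history.* The Day 1 rules in 7.9, 8.5.3, 9.8.1 and Table 6-1 say otherwise. A site following the schedule would record them.
- *Comparator-related events cannot be recorded.* They are reported like any other. What is missing is the attribution to the comparator.
- *A patient who leaves during a comparator period counts as a completer.* Section 6.6 already treats leaving the study early as non-completion, so 6.7 needs only its term aligned.

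Nor can the loss be sized from the 12% diarrhea rate. Section 8.1 applies that rate per subject to the whole study. In the appended labels it is 35 of 296 patients in Study 1, and the premarketing studies are described as lasting 48 weeks. It is not a rate per 28-day period.

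None of these arguments reaches causality. The Day 1 rules concern timing only, and none tells the investigator to judge relationship to Jadenu or Exjade.

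**Conclusion.** The concern holds as a moderate inconsistency in the recording rules, with its main weight on causality. On the protocol's only definition of the term, relationship to the comparator is not collected in any comparator period (up to 36 patients, 28 days each). The planned table of events by relationship to study medication would then lack its comparator half. The conflict over when adverse events start affects up to 18 comparator-first patients on paper. Actual loss of their events is unlikely.

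No bias in overall adverse-event counts has been shown, and none is claimed. The size of the effect on related events depends on how sites read 9.4, which the protocol leaves open in a multi-center trial. The conclusion assumes that no case report form instruction, none of which is shown, already directs causality to the treatment of the period. A statistical analysis plan could define how events are assigned to treatments, but it could not supply causality judgments that were not made at the site.

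**What to change.** - In 9.1, 9.2, 9.4 and 9.5, replace 'investigational product' with 'study treatment (DST-0509, Jadenu or Exjade)', and carry the same term into the relationship item of 9.8.1.
- In 9.1 and 9.2, start adverse-event status at the first dose of any study treatment on Day 1, in line with 7.9, 8.5.3 and Table 6-1.
- In 9.4 and 9.5, record causality and action taken against the study treatment of the current period or, for events in washout, of the most recent one.
- Align the term in 6.7 with 6.6.
- Keep 'investigational product' for DST-0509 supply and accountability in 5.1 and 5.2.

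The cost is protocol wording and one field label on the adverse-event form. It adds no visits, samples or patients. The change should be made before sites start recording events.
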